8.2. Analysis of Secondary Efficacy Endpoints

The secondary efficacy endpoint will be the responder rate, defined as the proportion of subjects who had at least a 50% reduction in the 28-day seizure rate for all PGTC seizures during the double-blind assessment phase, as measured from baseline (data collected during the 8-week baseline phase) on the ITT population. This secondary endpoint will be analyzed using a logistic regression model with the following fixed covariate terms: treatment, age stratum, and geographical region. No adjustments for multiplicity will be taken, and nominal p-values from 2-sided tests and the correspondence odds ratio with 95% confidence interval will be reported.

NOTE: The “PARAM=GLM” option in CLASS statement of SAS will be applied for logistic regression.

The responders and non-responders will be summarized descriptively by treatment using counts and percentages, and additionally by treatment group, age strata. Descriptive statistics for responder will also be provide for pediatrics overall (<17 years) and adults (17-65 years) and geographical region.

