2.1. Study Design

This study will consist of an 8-week baseline phase, a 12-week double-blind assessment phase (including a 2-week double-blind dose escalation phase and a 10-week double-blind fixed dose phase), and a 1-week double-blind taper phase. Eligible subjects will be randomly assigned to receive double-blind treatment with 1 of 2 dose levels of pregabalin or placebo. Study drug treatments are to be taken orally twice daily (BID) in equally divided doses for 12 weeks during the double-blind assessment phase and then 1 week double-blind taper. Subjects who complete the double-blind phase of this trial may be eligible for screening for a 1-year open-label pregabalin safety study.

A total sample size of 168 subjects (ie, 56 subjects per group) is needed to have been randomized, received treatment and had a baseline and post baseline efficacy assessment. Randomization will be stratified by site and subject age (Stratum 1: 5-7 years of age; Stratum 2: 8-11 years of age; Stratum 3: 12-16 years of age; Stratum 4: 17-65 years of age). Subjects in each age stratum within site will be randomized to a fixed dose of either placebo, Dose Level 1: pregabalin 5 mg/kg/day (maximum 300 mg/day) or Dose Level 2: pregabalin 10 mg/kg/day (maximum 600 mg/day) in a 1:1:1 ratio. Approximately 30% of planned enrollment (approximately 50 subjects) will be subjects <17 years of age. Every reasonable effort will be made to enroll a minimum of 12 subjects in each of the 4 age strata.

Study Design Diagram:

*Eligible subjects may be assessed for a 1-year open-label pregabalin safety study (Study A0081106) and complete end of study activities for A0081105 at Visit 10 (V10).

** Dose Level 1: 7 mg/kg/day for pediatric subjects <30 kg and 300 mg/day for subjects ≥ 17 years of age.

*** Dose Level 2: 14 mg/kg/day for pediatric subjects <30 kg and 600 mg/day for subjects ≥ 17 years of age.

Phone visits are also scheduled for Study Days 3, 10, 17, and 89 (each with a ± 3 day window).

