Based on a meta-analysis of double-blind placebo controlled adult adjunctive therapy studies (Studies 1008-009, 1008-011, and 1008-034) using the log transformed 28 day seizure rate, the expected differences from placebo (ie, the difference in the observed least squares means after adjusting out the study-to-study differences and site clustering within study effects) were -0.668 (-48.7%) and -0.448 (-36.1%) for 600 mg/day (Dose Level 2) and 300 mg/day (Dose Level 1), respectively. This study is powered on 80% of these estimated treatment differences; -0.534 (-41.4%) and -0.358 (-30.1%) for 600 mg/day (Dose Level 2) and 300 mg/day (Dose Level 1), respectively.

A meta-analysis of Studies 1008-009, 1008-011, and 1008-034 was used to estimate a pooled standard deviation of 0.73 on the log transformed 28 day seizure rate scale, with a 95% confidence interval of [0.70, 0.76]. For the purposes of this study, a smaller standard deviation of 0.67 was used to assess the power and initial sample size requirements for comparing the 2 pregabalin group to placebo. The rationale for assuming the smaller SD of 0.67 is based on the Study 1008-034 data which included all three treatment groups of interest (i.e., placebo, 300 mg/day, and 600 mg/day). This study had a point estimate for the standard deviation of 0.72 and a 95% confidence interval for the standard deviation of [0.67, 0.77].

To ensure that the sample size is reasonably sufficient using an assumed pooled standard deviation of 0.67 on the \log_e scale, in order to provide at least 80% power to detect a

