4. HYPOTHESES AND DECISION RULES

4.1. Statistical Hypotheses

There will be 2 pair-wise comparisons of interest:

- a) Dose Level 2: pregabalin 10 mg/kg/day (maximum 600 mg/day) - placebo, and*
- b) Dose Level 1: pregabalin 5 mg/kg/day (maximum 300 mg/day) - placebo.*

Each dose of pregabalin will be compared to placebo in a pair-wise manner using a sequential step-wise testing procedure to control for multiplicity of testing such that the experiment-wise type I error rate will not exceed the 5% level of significance.

1) The first step will test the null hypothesis of equal treatment effect of Dose Level 2 vs. placebo at $\alpha=0.05$ 2-sided for the primary endpoint.

$$H_{01}: \mu_{\text{PGB Dose Level 2}} - \mu_{\text{PBO}} = \mathbf{0}$$

$$H_{a1}: \mu_{\text{PGB Dose Level 2}} - \mu_{\text{PBO}} \neq \mathbf{0}$$

2) The second step will test the null hypothesis of equal treatment effect of Dose Level 1 vs. placebo at $\alpha=0.05$ 2-sided for the primary endpoint.

$$H_{02}: \mu_{\text{PGB Dose Level 1}} - \mu_{\text{PBO}} = \mathbf{0}$$

$$H_{a2}: \mu_{\text{PGB Dose Level 1}} - \mu_{\text{PBO}} \neq \mathbf{0}$$

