6.4. Covariates

Log-transformed 28-day seizure rate [$\log_e(28\text{-days seizure rate}_b + 1)$] at baseline will be utilized as a covariate in the linear model used in the primary analysis, and for secondary analyses utilizing a similar model.

Additional terms considered in the primary analysis and included in the responder rate analysis are age strata and geographic region. Because it is anticipated that this study will have many investigator centers having very few subjects in each treatment group, age strata, and geographic region combination; a pre-specified pooling will take place (See [below](#)).

Two covariates about age are defined as follows.

Age strata will be defined as Stratum 1: 5-7 years of age; Stratum 2: 8-11 years of age; Stratum 3: 12-16 years of age; or Stratum 4: 17-65 years of age. This covariate is applied to primary analysis.

Age group will be defined as: group 1, 5-16 years of age (at randomization); group 2: 17-65 years of age (at randomization). This covariate is applied to the analysis of primary efficacy endpoint as a sensitivity analysis. This age group definition will also be used to investigate treatment-by-age interaction for the primary efficacy endpoint.

Age will be defined as subjects' age at randomization. If a subject turns 66 at randomization after screening, he/she will be counted in the 17-65 age group.

Region will be defined as follows (Upon closing of the randomization, region determinations will be further evaluated-See [contingency plan](#)):

- *United States (US)*: Subjects who participate in the U.S. or Puerto Rico centers will be pooled together;
- *European Union*: All subjects who participate in European Union (eg, Austria, Belgium, Denmark, France, Germany, Greece, Italy, Netherlands, Portugal, Spain, Sweden, United Kingdom, Bulgaria, Croatia, Czech Republic, Estonia, Hungary, Lithuania, Poland, Romania, and Slovakia,) centers will be pooled together. The member countries of European Union are explained in more detail at https://europa.eu/european-union/about-eu/countries_en;
- *Asia-Pacific*: All subjects participating in Asia-Pacific (China, India, Korea, Malaysia, Philippines, Singapore) centers will be pooled together;
- *Others*: All subjects not participating in above three regions (eg, Russian Federation, Ukraine, Belarus, Bosnia and Herzegovina, Serbia, Montenegro, Turkey) centers will be pooled together.

Any region not enrolling any subjects will not be included in the analysis.

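### The responder-rate logistic model omits baseline PGTC seizure rate, which the SAP adjusts for in its primary, imputation and count models; adding it is cheap, with a gain that is probably small and cannot be derived from the documents

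*SAP*

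**What the plan says.** Section 8.2 fits responder status with "fixed covariate terms: treatment, age stratum, and geographical region". The responder row of the Section 8.5 table lists the same three terms.

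Section 6.4 says that the log baseline rate "will be utilized as a covariate in the linear model used in the primary analysis, and for secondary analyses utilizing a similar model". It then says that the additional terms "included in the responder rate analysis are age strata and geographic region". The word for additional leaves slight doubt whether baseline was also meant for the responder model, but Sections 8.2 and 8.5 settle the text: it is not there.

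Elsewhere the SAP does adjust for baseline:

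- Section 8.1: log baseline rate is in the primary ANCOVA and in both imputation models, and baseline seizure count is in the Poisson and negative binomial models.
- Section 8.5: the rank ANCOVA row lists ranked log baseline, and both seizure-free-day rows list their own baseline.
- Appendix 6: baseline rate, age strata and region are named together as important sources of variability, and all three enter the blinded residual variance.

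The responder rate has no power statement. Section 8.2 adds: "No adjustments for multiplicity will be taken, and nominal p-values from 2-sided tests".

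**The concern.** Section 6.1.2 defines response relative to the subject's own baseline, which can look like adjustment already made. It is only partly so. The baseline is a count over 8 weeks. A subject whose observed baseline happens to be high tends to fall back towards the usual level and so reaches a 50% reduction more easily; one whose observed baseline is low reaches it less easily. Responder status can therefore still depend on baseline.

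Randomisation is stratified by site and age (Section 2.1), not by seizure rate, so baseline balance between arms is left to chance. If the dependence is real, leaving it out costs some power and lets part of a chance imbalance show in the odds ratio.

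The SAP does not hold that a baseline-referenced outcome needs no adjustment. The number of seizure-free days gained is itself a change from baseline, and its row in Section 8.5 still includes baseline.

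**Working it through.** **1. Reproduce the plan's own figures.** Inputs are from Section 2.2: 56 per group, differences 0.534 and 0.358, SD 0.67 and 0.73, two-sided 0.05. Power = Φ{δ / (SD × √(2/56)) − 1.96}, with √(2/56) = 0.189.

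| δ | SD | Normal approximation | Noncentral t | Table 1 |
|---|---|---|---|---|
| 0.534 | 0.73 | 0.972 | 0.970 | 0.970 |
| 0.534 | 0.67 | 0.988 | 0.987 | 0.984 |
| 0.358 | 0.73 | 0.737 | 0.730 | 0.742 |
| 0.358 | 0.67 | 0.807 | 0.800 | 0.800 |

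Table 1 reproduces within 2 points. It concerns the primary endpoint only; there is no responder figure to reproduce.

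**2. When does dividing by baseline suffice?** A subject responds if log(r_t) − log(r_b) ≤ log(0.5) = −0.693. Suppose log(r_t) = a + b·log(r_b) + τ + e, where e has SD s. Then P(response) = Φ{[−0.693 − a − τ + (1 − b)·log(r_b)] / s}. Baseline drops out only if b = 1. With b below 1, response becomes more likely as observed baseline rises. The documents give no value for b. Appendix 6 defines a correlation without a value, and for the outcome variable of the re-estimation rather than for responder status.

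**3. Analytic range.** If baseline explains a share R² of responder status, a linear-model approximation gives: gain = Φ{(z_p + 1.96)/√(1 − R²) − 1.96} − p, where p is the unadjusted power and z_p its normal quantile. Example with assumed rates of 30% and 50% and 56 per arm: p = 0.581 and z_p + 1.96 = 2.1645. At R² = 0.05, 2.1645/0.9747 = 2.2207, and Φ(0.2607) = 0.603, a gain of 2.2 points. Over placebo rates of 25% to 45% and differences of 15 to 25 percentage points:

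- R² 0.01 to 0.02: +0.3 to +0.9 points
- R² 0.05 to 0.10: +1.5 to +4.6
- R² 0.20: +7.2 to +9.7

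**4. Simulation with the slope set freely.** The setup was 3 × 56 subjects, log(rate + 1) linear in baseline with normal error, age strata and region in both models, and 1,500 trials per setting. Assumed, not from the documents: baseline log(rate + 1) mean 1.6 and SD 0.6 or 0.9, minimum baseline rate 1.5 per 28 days, placebo shift −0.15, and no prognostic effect of age or region. Paired Monte Carlo error is roughly 0.5 point. Results at residual SD 0.67, in points of power:

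| Slope | Dose Level 1 | Dose Level 2 | Correlation of baseline with response |
|---|---|---|---|
| 1.1 | +0.2 to +0.5 | +0.3 to +0.5 | −0.139 to −0.163 |
| 1.0 | +0.3 to +0.9 | −0.1 to +0.3 | −0.075 to −0.085 |
| 0.8 | −0.6 to −0.4 | 0.0 | 0.030 to 0.065 |
| 0.6 | +2.0 to +2.1 | +0.3 to +1.3 | 0.140 to 0.204 |
| 0.4 | +3.0 to +6.2 | +1.8 to +4.2 | 0.236 to 0.320 |

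At residual SD 0.5 the gain runs from −0.3 to +7.9 (Dose Level 1) and from −0.1 to +2.1 (Dose Level 2). The small negative values are about the size of the Monte Carlo error.

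**5. Simulation with counts.** Slope and residual SD are not free of each other: the within-subject noise that widens the residual SD also flattens the slope. Count models, with log-normal subject rates and counts over 8 and 12 weeks, respect that link. All used 56 per arm; their rates, dispersion and entry thresholds are assumptions.

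| Setup | ANCOVA residual SD | Gain in points |
|---|---|---|
| Age and region in model | 0.36 to 0.52 | about 0 to 1 |
| Age and region in model | 0.62 to 0.65 | about 1.5 to 2.3 |
| Poisson counts, Dose Level 2 | 0.45 to 0.46 | +0.3 to +0.7 |
| Poisson counts, Dose Level 2 | 0.60 to 0.65 | +1.4 to +2.2 |
| Poisson counts, Dose Level 2 | 0.79 | +5.2 |
| Over-dispersed counts | 0.53 to 0.56 (slope 0.63 to 0.69) | +0.9 to +1.6 |
| Over-dispersed counts | 0.71 to 0.72 (slope 0.24 to 0.41) | +2.2 to +2.6 (Dose Level 1), +2.1 to +3.3 (Dose Level 2) |
| Over-dispersed counts | 0.81 to 0.94 | +1.1 to +3.1 (Dose Level 1), +2.3 to +5.4 (Dose Level 2) |

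Monte Carlo errors are about 0.4 to 0.8 point where recorded. The gains of 1.5 to 2.3 with age and region in the model are each within about 2 to 3 Monte Carlo standard errors of zero. In that setup type I error stayed near 5%.

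**The case against.** The choice is consistent: Sections 6.4, 8.2 and 8.5 agree, and Section 8.5 leaves baseline out of both logistic rows. Response is already scored against baseline, so much of the dependence is gone; with a slope of 0.8 to 1.0 in step 4, adjustment gains about 1 point or less. No decision hangs on it: Section 4.2 limits claims to the primary endpoint, the responder p-value is nominal, and the primary ANCOVA already adjusts. Chance imbalance under randomisation does not invalidate the test. Adding the term also changes the quantity estimated.

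All of this stands, and it makes the point an improvement rather than an error. It does not show that the omission is better. The odds ratio is already conditional on age and region, and no setting lost power beyond noise.

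Three stronger readings are tempting, and the documents support none of them.

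- *That the plan gives up 2 to 5 points of power.* A Dose Level 2 count simulation without age and region, at residual SD 0.68 to 0.80, does give differences from 0.508 − 0.489 = 1.9 points to 0.477 − 0.425 = 5.2 points. But the documents fix neither the responder rates nor the association. In the count models of step 5, gains near 5 points appear only at SD 0.79 or more, above the upper limits of 0.76 and 0.77 in Section 2.2. Step 4 exceeds 5 points only with an assumed slope of 0.4.
- *That baseline is the strongest covariate collected.* Appendix 6 names three terms without ranking them, and for the log seizure rate, not for response.
- *That baseline imbalance passes straight into the odds ratio.* Only the part left after dividing by baseline does so.

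**Conclusion.** The omission is real and out of line with the rest of the SAP, and dividing by baseline does not fully replace adjustment. Its size cannot be derived from the documents. Under the assumed count models, the gain in responder-rate power is roughly 0 to 1 point when within-subject variability is low and about 1.5 to 3 points near the planning SD.

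The second figure depends on reading the SD as a residual SD. Section 2.2 says only that "a smaller standard deviation of 0.67 was used to assess the power and initial sample size requirements" and gives 0.73 as the pooled estimate; it does not say that either is adjusted for baseline. The re-estimation in Section 2.2 and Appendix 6 does work with the ANCOVA residual variance, which makes the reading plausible but not certain.

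The point is low in priority. It affects the precision of one odds ratio and its nominal p-value. The primary analysis and its error control are untouched.

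**What to change.** Before unblinding, add log_e(baseline 28-day PGTC rate + 1) as a continuous term to the responder logistic model, and say so in Sections 6.4, 8.2 and 8.5. This also removes the slight doubt in Section 6.4. Section 8.3 models PGTC seizure-freedom in a way similar to the responder rate, so state explicitly whether that model takes the term too.

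The cost is one model term for a variable already derived in Appendix 1. The odds ratio becomes conditional on baseline as well as on age and region, so it is not the same quantity as the one now planned, and the report should say that. If the sponsor prefers to keep the present odds ratio, a prespecified sensitivity analysis with the baseline term is the minimum.

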8.3. Analysis of Exploratory Endpoints

The proportion of seizure-free days for each seizure type: PGTC, myoclonic, tonic/tonic, absence, and clonic seizures will utilize ANCOVA model.

The number of seizure-free days gained for each seizure type: PGTC, myoclonic, tonic/tonic, absence, and clonic seizures will be analyzed utilizing a linear model similar to the primary analysis.

The proportion of subjects with PGTC seizure-freedom will utilize a logistic regression model similar to the responder rate analysis.

No adjustments for multiplicity will be taken and nominal p-values from 2-sided tests will be reported.

The exploratory endpoints will additionally be presented descriptively overall, and separately by age group of pediatrics overall (<17 years) and adults (17-65 years).

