2. INTRODUCTION

Protocol A0081105 is a randomized, double-blind, parallel-group, placebo-controlled, multi-center trial in subjects 5 to 65 years of age with PGTC seizures. This study will evaluate the efficacy of 2 dose levels of pregabalin [Dose Level 1: pregabalin 5 mg/kg/day (maximum 300 mg/day) or Dose Level 2: pregabalin 10 mg/kg/day (maximum 600 mg/day), administered BID] compared with placebo.

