2.3. Study Objectives

Primary Objective:

- To demonstrate superior efficacy of pregabalin compared to placebo for treatment of PGTC seizures as measured by the 28 day seizure rate.*

Safety Objectives:

- To assess the safety and tolerability of pregabalin relative to placebo in pediatric and adult subjects with PGTC seizures.*

Secondary Objectives:

- To demonstrate superior efficacy of pregabalin compared to placebo for PGTC seizures as determined by responder rate.*

Exploratory Efficacy Objectives:

- To demonstrate superior efficacy of pregabalin compared to placebo as determined by seizure-free days for PGTC, myoclonic, tonic/tonic, absence, and clonic seizures.*

- *To demonstrate superior efficacy of pregabalin compared to placebo as determined by seizure-freedom of PGTC seizures over the last 28 days of the double-blind assessment phase and over the entire double-blind assessment phase. In those subjects with myoclonic, tonic/tonic, absence, or clonic seizures at baseline, seizure freedom over the last 28 days of the study and over the entire double-blind assessment phase will be summarized descriptively.*
- *To demonstrate superior efficacy of pregabalin compared to placebo as determined by the time to experience the same total number of PGTC seizures in the 12-week double-blind assessment phase that was observed during the baseline phase for each subject (referred to as 'Time to Nth Seizure'). This analysis will be reported separately from the main clinical study report.*

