5. ANALYSIS SETS

5.1. Full Analysis Set (Intent-to-Treat Population)

The efficacy analyses will be performed on the intent to treat (ITT) population which consists of randomized subjects who took at least 1 dose of investigational product during the double-blind assessment phase, have a baseline value and at least 1 post-baseline efficacy assessment (diary entry).

5.2. 'Per Protocol' Analysis Set (PP Population)

None. Protocol Deviations will be addressed (See [Section 5.6](#)) but no PP analyses are planned.

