6.1.3.2. Number of Seizure-Free Days Gained

The number of seizure-free days gained for each seizure type: PGTC, myoclonic, tonic/tonic, absence, and clonic seizures will be calculated. The number of seizure-free days will be adjusted to a per 12 weeks value (ie, 84 days) for the baseline and 12-week double-blind assessment phases. Changes from baseline are to be computed and the analysis performed accordingly. The 12 week adjusted number of seizure-free days is defined as follows:

number of seizure-free days in a period * 84 / (number of days in a period – number of missing diary days in a period) .

Period refers to the length time in baseline, and in DB. The 12 week adjusted number of seizure-free days will be calculated for baseline and DB; change from baseline will also be calculated.

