8. STATISTICAL METHODOLOGY AND STATISTICAL ANALYSES

The ITT population will be used in the analyses of the primary efficacy endpoint, and for all other efficacy endpoints. The Safety population will be used in the analyses of the safety data.

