8.5. Summary of Efficacy Analyses

Endpoint (Key Summary Metrics)	Analysis Set	Statistical Method	Model/ Covariates/ Strata	Missing Data	Interpretation
Log _e 28-day PGTC seizure rate (N, LS Mean Diff/SE)	ITT	ANCOVA	Treatment, region, age strata, baseline seizure rate	Days missing from Seizure Diary will be subtracted from rate calculations	Primary Analysis Note: age strata is protocol defined age strata. Baseline is the log of 28-day PGTC rate at baseline
Key summary statistics will be presented for the Log _e 28-day PGTC seizure rate and for the back transformed “percent reduction in seizures” relative to placebo.					
Log _e 28-day PGTC seizure rate (N, LS Mean Diff/SE) (treatment-by-age p-value)	ITT	ANCOVA	Treatment, region, age group, treatment-by-age group interaction, baseline seizure rate	Days missing from Seizure Diary will be subtracted from rate calculations	Supplemental Analysis Note: age groups are Age < 17 yrs and Age ≥ 17 yrs. Baseline is the log of 28-day PGTC rate at baseline.
Key summary statistics will be presented for the Log _e 28-day PGTC seizure rate and for the back transformed “percent reduction in seizures” relative to placebo.					
Responder rate (%)	ITT	Logistic regression	Treatment, region, age strata	Days missing from Seizure Diary will be subtracted from rate calculations	Secondary Analysis
Proportion Seizure-free days (%)	ITT	ANCOVA	Treatment, region, age strata, baseline	Days missing from Seizure Diary will be subtracted from rate calculations	Exploratory Analysis Each seizure type: PGTC, myoclonic, tonic/tonic, absence, and clonic seizures. Baseline for this endpoint is the proportion of seizure free days at baseline.
Number of seizure-free days gained (N, Mean, SE)	ITT	ANCOVA	Treatment, region, age strata, baseline	Days missing from Seizure Diary will be subtracted from rate calculations	Exploratory Analysis Each seizure type: PGTC, myoclonic, tonic/tonic, absence, and clonic seizures. Baseline for this endpoint is the number of adjusted seizure free days at baseline.

Proportion PGTC Seizure-freedom (%)	ITT	Logistic regression	Treatment, region, age strata	Days missing from Seizure Diary will be subtracted from rate calculations	Exploratory Analysis
Log _e 28-day PGTC seizure rate (N, LS Mean Diff/SE)	ITT	ANCOVA	Treatment, region, age strata, baseline	Multiple imputation will be applied.	Sensitivity Analysis. Baseline is the log of 28-day PGTC rate at baseline.

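### Seizure-free days for myoclonic, tonic, absence and clonic seizures are modelled only in the whole ITT set, so the plan never estimates the gain in patients who have the type

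*SAP*

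**What the plan says.** The trial population is defined by one seizure type: SAP Section 2 describes a "multi-center trial in subjects 5 to 65 years of age with PGTC seizures". Section 8 then sets a single analysis set for efficacy: "The ITT population will be used in the analyses of the primary efficacy endpoint, and for all other efficacy endpoints". Section 5.1 defines that set as "randomized subjects who took at least 1 dose of investigational product during the double-blind assessment phase" who also have a baseline value and at least one post-baseline diary entry. Seizure type plays no part in the definition.

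Section 8.3 applies an ANCOVA to the proportion of seizure-free days for five seizure types. For the second endpoint it says that "The number of seizure-free days gained for each seizure type: PGTC, myoclonic, tonic/tonic, absence, and clonic seizures will be analyzed utilizing a linear model". That model is patterned on the one for the primary endpoint. Both seizure-free-day rows of the Section 8.5 table name ITT and carry the note "Each seizure type: PGTC, myoclonic, tonic/tonic, absence, and clonic seizures". The model terms are treatment, region, age strata and baseline. For days gained, "Baseline for this endpoint is the number of adjusted seizure free days at baseline".

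Section 6.1.3.2 computes the score as "number of seizure-free days in a period * 84" divided by the days in the period less missing diary days, for baseline and for the double-blind phase, and then takes the change. Sections 6.1.3.1, 6.1.3.2, 8.3 and 8.5 and Appendix 1 contain no restriction to subjects who have the type in question.

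Such a restriction does appear for another endpoint. Section 2.3 limits the descriptive seizure-freedom summaries for the non-PGTC types: "In those subjects with myoclonic, tonic/tonic, absence, or clonic seizures at baseline, seizure freedom over the last 28 days of the study". The same limit covers the summary for the whole double-blind phase.

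**The concern.** A subject who never has, say, absence seizures does not drop out of the absence analysis as missing. The formula returns a valid score, at the ceiling, in both phases. Such subjects can show no gain on either treatment, yet they count fully in the mean. The fitted treatment difference is then an average over subjects who could gain days and subjects who could not.

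What is at stake is the meaning of the number. The endpoint is expressed in days gained, so its size is the message. As planned, that size depends on how common each type happened to be among those enrolled. A clinician treating a patient with absence seizures would want the gain among patients with absence seizures, and no planned analysis gives it. The model also assumes one residual variance across a group fixed at zero change and a group that varies.

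New onset adds a second difficulty. A subject free of the type at baseline can move only downwards, by losing days if the type emerges. Section 3.1 lists newly emergent generalized seizure types among the events for interim safety review, so the plan regards this as possible. Benefit in one group and emergence in the other end up in one estimate.

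**Working it through.** **Plan's own figures.** The SAP gives no expected gain, SD or power for seizure-free days, and no share of subjects with each type. Its one design calculation, Table 1, is reproduced to confirm the 56 per arm used below. With difference 0.358 and SD 0.67, the standard error is 0.67 × √(2/56) = 0.1266, so z = 0.358/0.1266 = 2.83. Power is Φ(2.83 − 1.96) = 0.807, or 0.800 with the noncentral t, against 0.800 stated.

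**Score of a never-affected subject (Section 6.1.3.2).** Every non-missing day is free of the type, so the score is 84 × (non-missing days)/(non-missing days) = 84 in each phase. The change is 84 − 84 = 0. This holds whatever the length of follow-up.

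**ITT difference.** Let p be the share with the type, D the treatment difference among them and E the difference among the rest. Then

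ITT difference = p × D + (1 − p) × E.

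With no new onset E = 0, so the ITT difference is p × D. For an assumed D of 6 days per 84:

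| p (assumed) | ITT difference, days | Affected per arm (56 × p) |
|---|---|---|
| 0.75 | 4.5 | 42 |
| 0.5 | 3.0 | 28 |
| 0.3 | 1.8 | 17 |
| 0.2 | 1.2 | 11 |

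The proportion endpoint behaves in the same way. The days score is 84 times the proportion, so 6 days is 6/84 = 7.1 percentage points, and 1.2 to 4.5 days is 1.4 to 5.4 points.

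**Does the baseline covariate remove the shrinkage?** It does not, because the model fits one common treatment effect. A simulated ANCOVA confirms this (4,000 runs per p, two arms of 56, baseline covariate only, 56 baseline and 84 double-blind days, an assumed 30% cut in seizure-day probability among affected subjects, no new onset). The restricted analysis used subjects with at least one seizure of the type at baseline.

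| p | ITT estimate | Restricted estimate | Ratio | Power, ITT vs restricted |
|---|---|---|---|---|
| 0.75 | 3.67 | 4.97 | 0.74 | 0.63 vs 0.63 |
| 0.5 | 2.44 | 4.99 | 0.49 | 0.44 vs 0.45 |
| 0.3 | 1.45 | 5.03 | 0.29 | 0.27 vs 0.28 |
| 0.2 | 0.93 | 4.91 | 0.19 | 0.18 vs 0.19 |

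The ratio tracks p, and power hardly moves.

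**Rare types under the full model.** The planned model has 1 intercept + 2 treatment + 3 region + 3 age + 1 baseline = 10 parameters. At p = 0.1, about 0.1 × 168 = 17 subjects remain over three arms, leaving about 17 − 10 = 7 residual degrees of freedom. Simulation of that model, with assumed region and age shares, showed lower power for the restricted analysis than for ITT. In about 3% of runs the contrast could not be estimated. The power levels depend heavily on the assumed inputs, so only the direction is used here. At p of 0.3 or more the loss was small.

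**The case against.** The strongest reply is that this is partly a choice of estimand. The ITT mean answers how many days free of a given type the treated PGTC population gains or loses. It keeps everyone randomized who meets the ITT definition, and it counts new onset, which a baseline-positive subset leaves out of the model. That stands. It argues for keeping the ITT result, but it does not supply the gain among patients who have the type.

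Four stronger readings are tempting, and the documents do not support them.

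- A reader might infer that the plan contradicts itself, because Section 2.3 restricts seizure freedom to subjects with the type at baseline. That restriction belongs to a different, descriptive, yes/no outcome, in which a never-affected subject would count as a success. For days gained the same subject contributes zero. Section 2.3 words the seizure-free-days objective without restriction, and Sections 8.3 and 8.5 follow it.
- A reader might infer that most subjects lack each type, or that a useful effect would be reported as trivial. The SAP gives no shares, no expected gain and no threshold for a trivial one.
- A reader might treat the change as exactly zero for everyone free of the type at baseline. New onset breaks that. So does Appendix 1, whose formula for days gained omits the missing-diary subtraction: a never-affected subject with m missing days in an 84-day phase would score 84 − m if missing days are not counted as seizure-free.
- A reader might conclude that restricting costs no power at all. That holds in the simulation for p of 0.2 and above with a baseline covariate, but not for a very rare type under the full model.

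Consequence is also limited. Section 8.3 gives these endpoints nominal p-values only, Section 4.2 confines treatment claims to the primary endpoint, and the PGTC versions of both endpoints are unaffected.

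**Conclusion.** The concern holds as a matter of interpretation, and it is minor. For the four non-PGTC types, both seizure-free-day endpoints are planned only in the whole ITT set. The resulting difference is about p times the difference among affected subjects: 1.2 to 4.5 days for an assumed 6-day gain and assumed p of 0.2 to 0.75.

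The multiplication by p rests on no new onset and on the Section 6.1.3.2 formula. The direction, toward zero, holds for any p below 1 under those conditions. With new onset the estimate also carries the term (1 − p) × E, which may have either sign depending on which arm sees more emergence.

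The ITT contrast remains a valid randomized comparison, and the test itself is little affected. The primary and secondary analyses are untouched. This rests on the SAP text; if the protocol's eligibility criteria require any of the other types, p for that type would be near 1 and the point would fall away for it.

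**What to change.** Keep the ITT analysis and add the following to Sections 8.3 and 8.5 for each of the four non-PGTC types:

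- Analyse both the proportion of seizure-free days and the days gained in ITT subjects with at least one seizure of that type during the baseline phase. Report this beside the ITT result with N per arm. Because the restriction uses a pre-randomization characteristic, the comparison stays randomized.
- Summarise new onset by arm among subjects with no seizure of that type during baseline.
- State in advance the subset size below which only descriptive statistics are given, set with the roughly 10 parameters of the full model in mind.
- Reconcile the days-gained formula in Appendix 1 with Section 6.1.3.2 on missing diary days.

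The cost is a few sentences, extra tables and a size threshold to agree. No new data are needed beyond the seizure-type records that these endpoints already use. The downside is small numbers and some loss of precision for rare types, where the result may be descriptive only.
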